### **7.3. Lost to Follow up**

A participant will be considered lost to follow-up if he or she repeatedly fails to return for scheduled visits and is unable to be contacted by the study site.

The following actions must be taken if a participant fails to return to the clinic for a required study visit:

- The site must attempt to contact the participant and reschedule the missed visit as soon as possible and counsel the participant on the importance of maintaining the assigned visit schedule and ascertain whether or not the participant wishes to and/or should continue in the study.
- Before a participant is deemed lost to follow up, the investigator or designee must make every effort to regain contact with the participant (where possible, 3 telephone calls and, if necessary, a certified letter to the participant's last known mailing address or local equivalent methods). These contact attempts should be documented in the participant's medical record.
- Should the participant continue to be unreachable, he/she will be considered to have withdrawn from the study.

Discontinuation of specific sites or of the study as a whole are handled as part of Appendix 1.

## **8. STUDY ASSESSMENTS AND PROCEDURES**

- Study procedures and their timing are summarized in the SoA. Protocol waivers or exemptions are not allowed.
- Immediate safety concerns should be discussed with Pfizer immediately upon occurrence or awareness to determine if the participant should continue or discontinue study intervention.
- Adherence to the study design requirements, including those specified in the SoA, is essential and required for study conduct.
- All screening evaluations must be completed and reviewed to confirm that potential participants meet all eligibility criteria. The investigator will maintain a screening log to record details of all participants screened and to confirm eligibility or record reasons for screening failure, as applicable.
- Procedures conducted as part of the participant's routine clinical management (eg, blood count) and obtained before signing of the ICF may be utilized for screening or baseline purposes provided the procedures met the protocol-specified criteria and were performed within the time frame defined in the SoA.

### **8.1. Efficacy Assessments**

No formal efficacy evaluations will be performed. However, the following information will be collected for exploratory efficacy evaluations:

- Vector-derived FIX:C activity levels (including peak and steady-state levels)
- FIX antigen level

- Annualized bleed rate (ABR) (spontaneous and traumatic)
- Annualized factor IX consumption
- Health-economic parameters ([Section 8.9](#))
- Number of target joints ([Section 8.10.3](#))
- Health-related quality-of-life ([Section 8.10.4](#))
- Changes in level of activity ([Section 8.10.5](#))

## **8.2. Safety Assessments**

Planned time points for all safety assessments are provided in the SoA.

### **8.2.1. Physical Examinations**

Physical examination including height and weight.

### **8.2.2. Vital Signs**

Vital sign measurements including blood pressure, pulse rate, respiratory rate, and temperature (°C/°F), and should be taken after the subject has been resting supine or upright for 5 minutes.

### **8.2.3. Electrocardiograms**

Electrocardiograms (ECG) for participants >50 years of age or if clinically indicated.

### **8.2.4. Clinical Safety Assessments**

- Hemophilia medical history for the 26 weeks preceding screening.
- Target joint history for the 52 weeks preceding screening. Target joints will be identified and assessed during this study. A target joint is defined as a major joint (eg, hip, elbow, wrist, shoulder, knee, ankle) into which repeated bleeding occurs (frequency of 3 or more bleeding episodes into the same joint in a consecutive 12 week period) and with symptoms of pre-existing target joint involvement (eg, synovitis, persistent swelling, effusion, limitation of range of motion) (Ota et al. 2007).
- Assessment for adverse signs and symptoms (AE and SAE recording) and concomitant medications
- Concomitant therapy and procedures

### **8.2.5. Clinical Safety Laboratory Assessments**

- See [Appendix 2](#) for the list of clinical laboratory tests to be performed and to the SoA for the timing and frequency.

- The investigator must review the laboratory report, document this review, and record any clinically relevant changes occurring during the study in the AE section of the CRF. The laboratory reports must be filed with the source documents. Clinically significant abnormal laboratory findings are those which are not associated with the underlying disease, unless judged by the investigator to be more severe than expected for the participant's condition.
- All laboratory tests with values considered clinically significantly abnormal during participation in the study or within  $52 \pm 2$  weeks after the last dose of study intervention should be repeated until the values return to normal or baseline or are no longer considered clinically significant by the investigator or medical monitor.
- If such values do not return to normal/baseline within a period of time judged reasonable by the investigator, the etiology should be identified and the sponsor notified.
- All protocol-required laboratory assessments, as defined in Appendix 2, must be conducted in accordance with the laboratory manual and the SoA.
- If laboratory values from non-protocol specified laboratory assessments performed at the institution's local laboratory require a change in participant management or are considered clinically significant by the investigator (eg, SAE or AE or dose modification), then the results must be recorded in the CRF.

### **8.3. Adverse Events and Serious Adverse Events**

The definitions of an AE or SAE can be found in Appendix 3.

AE will be reported by the participant (or, when appropriate, by a caregiver, surrogate, or the participant's legally authorized representative).

The investigator and any qualified designees are responsible for detecting, documenting, and recording events that meet the definition of an AE or SAE and remain responsible to pursue and obtain adequate information both to determine the outcome and to assess whether it meets the criteria for classification as an SAE, or that caused the participant to discontinue the study ([Section 7.2](#))

In addition, the investigator may be requested by Pfizer Safety to obtain specific follow-up information in an expedited fashion.

#### **8.3.1. Time Period and Frequency for Collecting AE and SAE Information**

The time period for actively eliciting and collecting AEs and SAEs ("active collection period") for each participant begins from the time the participant provides informed consent, which is obtained before the participant's participation in the study (ie, before undergoing any study-related procedure and/or receiving investigational product), through and including last study visit.

For participants who are screen failures, the active collection period ends when screen failure status is determined.

Medical occurrences that begin before the start of study intervention but after obtaining informed consent will be recorded on the Medical History/Current Medical Conditions section of the case report form (CRF) not the AE section.

Follow up by the investigator continues throughout and after the active collection period and until the event or its sequelae resolve or stabilize at a level acceptable to the investigator, and Pfizer concurs with that assessment.

Investigators are not obligated to actively seek AE or SAE after conclusion of the study participation. However, if the investigator learns of any SAE, including a death, at any time after a participant has been discharged from the study, and he/she considers the event to be reasonably related to the study intervention or study participation, the investigator must promptly notify the sponsor.

#### **8.3.1.1. Reporting SAEs to Pfizer Safety**

All SAEs occurring in a participant during the active collection period are reported to Pfizer Safety on the CT SAE Report Form immediately and under no circumstance should this exceed 24 hours, as indicated in Appendix 3. The investigator will submit any updated SAE data to Pfizer within 24 hours of it being available.

All SAEs occurring in a participant during the active collection period are reported to Pfizer Safety on the CT SAE Report Form.

SAEs occurring in a participant after the active collection period has ended are reported to Pfizer Safety if the investigator becomes aware of them; at a minimum, all SAEs that the investigator believes have at least a reasonable possibility of being related to investigational product must be reported to Pfizer Safety.

#### **8.3.1.2. Recording Non-serious AEs and SAEs on the CRF**

During the active collection period, both non-serious AEs and SAEs are recorded on the CRF.

#### **8.3.2. Method of Detecting AEs and SAEs**

The method of recording, evaluating, and assessing causality of AE and SAE and the procedures for completing and transmitting SAE reports are provided in Appendix 3.

Care will be taken not to introduce bias when detecting AEs and/or SAEs. Open-ended and non-leading verbal questioning of the participant is the preferred method to inquire about AE occurrences.

#### **8.3.3. Follow-up of AEs and SAEs**

After the initial AE/SAE report, the investigator is required to proactively follow each participant at subsequent visits/contacts. For each event, the investigator must pursue and

obtain adequate information until resolution, stabilization, the event is otherwise explained, or the participant is lost to follow-up (as defined in [Appendix 3](#)).

In general, follow-up information will include a description of the event in sufficient detail to allow for a complete medical assessment of the case and independent determination of possible causality. Any information relevant to the event, such as concomitant medications and illnesses, must be provided. In the case of a participant death, a summary of available autopsy findings must be submitted as soon as possible to Pfizer Safety.

Further information on follow-up procedures is given in [Appendix 3](#).

#### **8.3.4. Regulatory Reporting Requirements for SAEs**

- Prompt notification by the investigator to the sponsor of a SAE is essential so that legal obligations and ethical responsibilities towards the safety of participants and the safety of a study intervention under clinical investigation are met.
- The sponsor has a legal responsibility to notify both the local regulatory authority and other regulatory agencies about the safety of a study intervention under clinical investigation. The sponsor will comply with country-specific regulatory requirements relating to safety reporting to the regulatory authority, institutional review boards (IRB)/independent ethics committees (IEC), and investigators.
- Investigator safety reports must be prepared for suspected unexpected serious adverse reactions (SUSAR) according to local regulatory requirements sponsor policy and forwarded to investigators as necessary.
- An investigator who receives an investigator safety report describing a SAE or other specific safety information (eg, summary or listing of SAEs) from the sponsor will review and then file it along with the Investigator's Brochure and will notify the IRB/IEC, if appropriate according to local requirements.

#### **8.3.5. Exposure During Pregnancy or Breastfeeding, and Occupational Exposure**

Exposure to the investigational product under study during pregnancy or breastfeeding and occupational exposure are reportable to Pfizer Safety within 24 hours of investigator awareness.

##### **8.3.5.1. Exposure During Pregnancy**

- Details of all pregnancies in female partners of male participants will be collected after the start of study intervention and until end of study participation.
- If a pregnancy is reported, the investigator should inform the sponsor within 24 hours of learning of the pregnancy and should follow the procedures outlined in [Appendix 4](#).
- Abnormal pregnancy outcomes (eg, spontaneous abortion, fetal death, stillbirth, congenital anomalies, ectopic pregnancy) are considered SAEs.

### **8.3.5.2. Exposure During Breastfeeding**

Scenarios of exposure during breastfeeding must be reported, irrespective of the presence of an associated SAE, to Pfizer Safety within 24 hours of the investigator's awareness, using the CT SAE Report Form. An exposure during breastfeeding report is not created when a Pfizer drug specifically approved for use in breastfeeding women (eg, vitamins) is administered in accord with authorized use. However, if the infant experiences an SAE associated with such a drug's administration, the SAE is reported together with the exposure during breastfeeding.

### **8.3.5.3. Occupational Exposure**

An occupational exposure occurs when, during the performance of job duties, a person (whether a healthcare professional or otherwise) gets in unplanned direct contact with the product, which may or may not lead to the occurrence of an AE.

An occupational exposure is reported to Pfizer Safety within 24 hours of the investigator's awareness, using the CT SAE Report Form, regardless of whether there is an associated SAE. Since the information does not pertain to a participant enrolled in the study, the information is not recorded on a CRF; however, a copy of the completed CT SAE Report Form is maintained in the investigator site file

### **8.3.6. Disease-Related Events and/or Disease-Related Outcomes Not Qualifying as AEs or SAEs**

The disease related events (DREs) for this study include episodes of bleeding related to hemophilia B. The bleeding episode itself is not reported as an AE, unless the bleeding episode meets the criteria outlined below.

Consideration on whether the bleeding event is a DRE is based on investigator determination and bleeding events recorded by the participant in their electronic diary will be reviewed by the investigator and assessed against reporting obligations for S/AE.

Bleeding, not due to the participant's hemophilia, will be recorded as an AE, and not a DRE.

If any of the following conditions apply, then the event must be recorded and reported as an AE or SAE (instead of a DRE):

- Bleeding events that require hospitalization or meet other SAE criteria ([Section 10.3](#)) should be reported as SAEs. When bleeding episodes that meet the SAE criteria are recorded on the AE CRF, the location (site) of the bleed and the etiologic classification as spontaneous or traumatic should be included.
- The bleeding event is, in the investigator's opinion, of greater intensity, frequency, or duration than expected for the individual participant.

OR

- The investigator considers that there is a reasonable possibility that the bleeding event was related to study intervention.

### 8.3.7. Medication Errors

Medication errors may result from the administration or consumption of the investigational product by the wrong participant, or at the wrong time, or at the wrong dosage strength.

Exposures to the investigational product under study may occur in clinical trial settings, such as medication errors.

Safety Event	Recorded on the CRF	Reported on the CT SAE Report Form to Pfizer Safety Within 24 Hours of Awareness
Medication errors	All (regardless of whether associated with an AE)	Only if associated with an SAE

Medication errors include:

Medication errors involving participant exposure to the investigational product;

Potential medication errors or uses outside of what is foreseen in the protocol that do or do not involve the participating participant.

Such medication errors occurring to a study participant are to be captured on the medication error page of the CRF, which is a specific version of the AE page.

In the event of a medication dosing error, Pfizer should be notified immediately.

Whether or not the medication error is accompanied by an AE, as determined by the investigator, the medication error is recorded on the medication error page of the CRF and, if applicable, any associated AE(s), serious and non-serious, are recorded on an AE page of the CRF.

Medication errors should be reported to Pfizer Safety within 24 hours on a CT SAE Report Form only when associated with an SAE.

### 8.4. Treatment of Overdose

An overdose is any dose more than the intended dose of investigational product given to a participant. Overdoses are not considered AEs; however, all overdoses should be recorded on an SAE form and faxed to Pfizer Safety within 24 hours. An overdose should be reported even if it does not result in an AE. Overdoses do not need to be recorded as AEs but any symptoms of an overdose should be reported in the eCRF as AEs; dosing information is recorded on an eCRF.

For this study, any dose of PF-06838435 greater than the intended dose of  $1 \times 10^{12}$  vg/kg or  $2 \times 10^{12}$  vg/kg of the body weight will be considered an overdose.

Sponsor does not recommend specific treatment for an overdose.

In the event of an overdose, the investigator/treating physician should:

- Contact the Medical Monitor immediately.
- Closely monitor the participant for any AE/SAE and laboratory abnormalities.
- Document the quantity of the excess dose as well as the duration of the overdose in the CRF.
- Overdose is reportable to Safety **only when associated with a SAE**.

### 8.5. Pharmacokinetics

All samples collected from participants for plasma factor IX activity levels will be analyzed at a certified clinical laboratory by one-stage assay. Results will be used to determine peak, and steady-state vector-derived circulating FIX activity levels.

CCI [REDACTED]

CCI [REDACTED]

[REDACTED]

CCI [REDACTED]

[REDACTED]

[REDACTED]

CCI [Redacted]

[Redacted]

CCI [Redacted]

[Redacted]

CCI [Redacted]

[Redacted]

[Redacted]

[Redacted]

[Redacted]

[Redacted]

[Redacted]

CCI [Redacted]

[Redacted]

[Redacted]

[Redacted]

[Redacted]

[Redacted]

[Redacted]

CCI [Redacted]

[Redacted]

[Redacted]

[Redacted]

CCI [Redacted]

[Redacted]

CCI [Redacted]

[Redacted]

[Redacted]

[Redacted]

CCI [REDACTED]

[REDACTED]

[REDACTED]

[REDACTED]

[REDACTED]

[REDACTED]

[REDACTED]

[REDACTED]

CCI [REDACTED]

[REDACTED]

[REDACTED]

[REDACTED]

[REDACTED]

[REDACTED]

CCI [REDACTED]

[REDACTED]

## 9. STATISTICAL CONSIDERATIONS

The details of statistical methodology are specified in the Statistical Analysis Plan (SAP). In general, statistical analyses will be primarily descriptive in nature. Summary statistics will be presented for all safety, PK and efficacy endpoints (including vector-derived FIX:C activity levels over time after PF-06838435 administration, annualized bleeding rate, etc.).

No formal statistical hypothesis testing will be performed. Various exploratory statistical tests may be applied to data generated from this study to generate hypotheses to be tested in subsequent trials.

**9.1. Estimands and Statistical Hypotheses**

**9.1.1. Estimands**

As the primary study objective is the assessment of safety and tolerability of a single IV infusion of PF-06838435; the estimands are defined here only for the secondary objective of the study. This study aims to characterize kinetics of PF-06838435 after a single dose administration in the population of participants meeting study’s inclusion/exclusion criteria. The vector-derived endogenous (not affected by intercurrent FIX product infusions) FIX:C activity levels will be characterized by post-treatment population mean. The assessment will be done for each dose of PF-06838435. Since only a single IV infusion of PF-06838435 will be administered during the study, there should be no treatment discontinuations. There may be missing data, including those from participants lost to follow-up, but it is anticipated to be rare. The handling of missing data is discussed in SAP.

**9.1.2. Statistical Hypotheses**

No formal hypotheses will be tested in this study.

**9.2. Sample Size Determination**

No formal hypotheses will be tested in this study. The sample size is based on the need to establish the initial safety and kinetic profile of PF-06838435 and select dose for the proper efficacy assessment. Approximately 20 participants will be dosed in the study.

**9.3. Populations for Analyses**

For purposes of analysis, the following populations are defined:

Population	Description
Enrolled	All participants who sign the ICF.
Dosed	All participants who were enrolled and received a single intravenous infusion of PF-06838435.
Evaluable	All dosed participants.
Safety	All dosed participants.

Defined sets for analysis	Description
Safety Analysis Set	All dosed participants.
Pharmacokinetics Analysis Set	All dosed participants who have collected vector-derived factor IX in circulation (FIX:C) activity levels enabling acceptable determination of the peak and steady-state derived activity level.
CCI	

Defined sets for analysis	Description
FIX Incremental Recovery Analysis Set	All dosed participants who have received 100 IU/kg of FIX protein product infusion and have completed the blood sample collection 30 (±2) min post infusion for FIX protein product enabling determination of FIX incremental recovery.

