13. LFTs – albumin, total bilirubin, direct bilirubin, indirect bilirubin, alkaline phosphatase (ALP), aspartate aminotransferase (AST), alanine aminotransferase (ALT), total protein, gamma-glutamyl transferase (GGT), and lactate dehydrogenase (LDH);

Immunology - CPT™ for PBMC by ELISPOT and PAXgene for RNA. PAXgene samples will be stored for analysis at the end of study.

14. Hepatic transaminases and FIX transgene expression will be monitored twice-weekly or thrice-weekly to detect early changes. Between Weeks 1 and 12 post-vector infusion, monitoring will include LFTs, FIX:C, FIX Ag, CPT™ for PBMC by ELISPOT and PAXgene for RNA. Spare plasma, from already collected blood samples will be stored for repeat or additional tests. Some participants may need more frequent monitoring using unscheduled visits.
15. Activated partial thromboplastin time (aPTT) measured in seconds; TAT will be taken just prior to the infusion of FIX product.
16. Participants should be advised to temporarily suspend prophylaxis regimen after vector infusion until being advised by the Investigator to resume.
17. At Day 0, participants should arrive at the clinic with at least 96 hours (4 days) washout of pd-FIX/rFIX or up to 168 hours (7 days) washout of extended half-life FIX product. Participants will receive a single IV infusion of 100 IU/kg of FIX protein product over 10 (±2) minutes.
18. Blood samples will be collected at pre-infusion, 10 (±2) minutes, 1 hour ± 10 minutes, 3 hours ± 10 minutes, 6 hours ± 10 minutes, and 24 (±1) hours from the start-of-infusion of FIX protein product.
19. Thromboelastography (TEG) and/or rotational thromboelastogram (ROTEM) – Only selected participants at selected sites capable of performing these tests locally.  
CCI  
Blood samples will be collected at pre-infusion and 10 (±2) minutes from the start-of-infusion of FIX protein product on Day 0 and End-of-Study Visits.
20. After the completion of FIX protein product infusion, participants will receive PF-06838435 infused via infusion pump over a period of approximately 60 minutes.
21. Haem-A-QoL, EQ-5D-5L, McGill pain questionnaire, and Hemophilia Activities List (including Changes in Level of Activity) questionnaires will be completed by the participants.  
CCI  
[REDACTED]
23. Immunomodulation See [Appendix 2](#): possible tests below:  
LFT – albumin, total bilirubin, direct bilirubin, indirect bilirubin, ALP, AST, ALT, total protein, GGT, and LDH;  
Coagulation –aPTT, FIX:C, FIX Ag  

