As the primary study objective is the assessment of safety and tolerability of a single IV infusion of PF-06838435, the estimands are defined here only for the secondary objective of the study. This study aims to characterize kinetics of PF-06838435 after a single dose administration in the population of participants meeting study's inclusion/exclusion criteria. The vector-derived endogenous (not affected by intercurrent FIX product infusions) FIX:C activity levels will be characterized by post-treatment population mean. The assessment will be done for each dose of PF-06838435. Since only a single IV infusion of PF-06838435 will be administered during the study, there should be no treatment discontinuations. There may be missing data, including those from participants lost to follow-up, but it is anticipated to be rare. The handling of missing data is discussed in the Statistical Analysis Plan (SAP).

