##### 9.4.1. Efficacy Analyses

Endpoint	Statistical Analysis Methods
Primary	No primary efficacy endpoints.
Secondary	
 
Vector-derived steady state FIX activity level will be analyzed in PK analysis set by dose level.
 
Vector-derived peak FIX activity level will be analyzed in PK analysis set by dose level.
 
FIX antigen levels will be analyzed in PK analysis set by dose level.
 

CCI	
 
[Redacted]
 
[Redacted]
 
[Redacted]
 
[Redacted]
 

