Study day, that is the start/stop date of an event, will be calculated as (date of event – first PF-06838435 infusion date) if event date is prior to PF-06838435 infusion date; Study Day will be calculated as (date of event – first PF-06838435 infusion date+1) if event date is on or after PF-06838435 infusion date.

Unscheduled visits will not be included in table summaries but will be included in the data listings.

Handling of incomplete or missing data:

No imputation will be applied for missing data for the analyses of safety or efficacy endpoints.

Data presentations:

Disposition and safety analyses will be presented for all subjects. All efficacy analyses will be presented overall and by regimen (prophylaxis and on-demand) as appropriate.

All analyses will be conducted using SAS version 9.2 or higher.

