4.3. Analysis Set

4.3.1. Safety Analysis Set

The safety analysis set is defined as all subjects who receive the infusion of PF-06838435. The analysis of safety and efficacy will be performed in this population.

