4.3.3. Pharmacokinetics (PK) Analysis Set

The PK analysis set will include subjects who have received PF-06838435 and have collected vector-derived FIX:C activity levels enabling acceptable determination of the peak and steady-state derived activity level.

CCI

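### The PK analysis set requires both peak and steady-state FIX:C, so a participant without a steady-state value may also drop out of the peak and antigen summaries

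*Protocol*

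**What the plan says.** **Who is in the set.** Protocol 9.3 admits dosed participants with FIX:C "activity levels enabling acceptable determination of the peak and steady-state derived activity level". SAP 4.3.3 sets the same condition: subjects must "have collected vector-derived FIX:C activity levels enabling acceptable determination of the peak and steady-state derived activity level". Both levels must be determinable. The visible text does not say what makes a determination acceptable.

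**What is analysed in it.** Protocol 9.4.1 states: "Vector-derived steady state FIX activity level will be analyzed in PK analysis set by dose level". It uses the same set for peak FIX:C, and for antigen: "FIX antigen levels will be analyzed in PK analysis set by dose level".

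**What a steady state needs.** Protocol 4.1.3.1 asks for two washed-out readings at least two weeks apart, starting from Week 8-12. SAP 3.1 takes an average of washed-out readings from Week 12.

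**What is being estimated.** Protocol 3 and 9.1.1 define the secondary estimand as a post-treatment mean at each dose, unaffected by intercurrent FIX infusions, "in the population of participants meeting study's inclusion/exclusion criteria". Missing data are expected to be rare and are left to the SAP, which states in its Section 4: "No imputation will be applied for missing data for the analyses of safety or efficacy endpoints".

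**Which set governs in the SAP.** SAP 4.3.1 says of the safety set (all dosed): "The analysis of safety and efficacy will be performed in this population". SAP 10.2, on vector-derived FIX:C, names no set. The protocol treats FIX:C as an efficacy measure (8.1, 9.4.1).

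**The concern.** Membership depends on data collected after the infusion, while the estimand covers everyone eligible and treated. Two routes out of the set are open:

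- **Early withdrawal.** Someone who leaves before the window has no steady-state value.
- **Too few washed-out readings.** Schedule of Activities note 16 has participants "temporarily suspend prophylaxis regimen after vector infusion until being advised by the Investigator to resume". Regular FIX dosing after that point reduces the number of washed-out readings.

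On either route the participant may also lose peak and antigen values that were measured. Schedule of Activities note 14 has FIX:C and antigen followed two or three times a week in Weeks 1 to 12, so a peak may well have been observed. Nothing in the documents justifies dropping an observed peak because a different quantity is missing.

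For the steady-state summary the issue is selection. If the missing participants are those whose expression failed, the summary describes maintained expressers only. Protocol 9.2 gives dose selection as one purpose of the study.

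**Working it through.** The plan gives no figure to reproduce. There is no hypothesis test, SD, dropout rate or expected FIX:C level for this product. The check is a reading of the rules followed by an illustration on assumed inputs.

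**Step 1: follow a participant through the rules.**

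- Withdraws at Week 6 with peak and antigen measured: no reading falls in either document's window, so steady state is not determinable. He is out of the PK set, and under protocol 9.4.1 out of all three summaries.
- Loses expression but has two washed-out low readings in the protocol's window: steady state is determinable and low. He stays in, provided that low readings are accepted as a determination. The text does not say so.
- Resumes regular FIX product with fewer than two washed-out readings in the protocol's window: he may leave the set.

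**Step 2: is loss of expression around the window plausible?** The protocol's Synopsis (Rationale) reports an earlier AAV8 study in which two of three participants lost expression at about 2-4 months. At 52/12 = 4.33 weeks a month, that is about Week 8.7 to Week 17.3, which overlaps the window. Protocol 4.1.3.1 itself allows for a decline to baseline through an immune response.

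**Step 3: size for steady state.** Let *n* be the number dosed, *k* the number excluded, *m* the level in those retained (all set equal) and *l* the level in those excluded.

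- PK-set mean = *m*
- All-dosed arithmetic mean = [(*n* - *k*)*m* + *k l*]/*n*
- All-dosed geometric mean = exp{[(*n* - *k*) ln *m* + *k* ln *l*]/*n*}

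Inputs: *n* = 20 (protocol 9.2), *l* = 2% (the entry ceiling, used as the level after complete loss), and *m* = 30% and *k* as assumptions.

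- *k* = 2, arithmetic: (18 × 30 + 2 × 2)/20 = 544/20 = 27.2%. The PK-set value of 30% is 30/27.2 = 1.10 times this.
- *k* = 2, geometric: 30 × (2/30)^(2/20) = 22.9%, a ratio of 1.31.
- A cohort of 5 with *k* = 1, arithmetic: (4 × 30 + 2)/5 = 24.4%. Geometric: 30 × (2/30)^(1/5) = 17.5%.

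Relative overstatement for *n* = 20, *m* from 12% to 40% and *l* from 1% to 2%:

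| Excluded | Arithmetic mean | Geometric mean |
|---|---|---|
| 1 | 4.3-5.1% | 9.4-20.3% |
| 2 | 9.1-10.8% | 19.6-44.6% |
| 4 | 20.0-24.2% | 43.1-109.1% |

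Both scales are shown because the estimand is a population mean, while SAP 10.2 works with geometric means and is unclear about how they are combined across a dose group.

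**Step 4: exclusions not caused by lost expression.** Take *m* = 27%. If those excluded also had 27%, the bias is zero. If they had 40%, the all-dosed arithmetic mean is 27.65% (*k* = 1) or 28.3% (*k* = 2), and the PK-set mean is too low by 2.4% or 4.6%.

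**Step 5: responder counts.** If 18 of 20 have a determinable steady state and all 18 exceed 5%, the PK set shows 18/18 = 100% and all dosed shows 18/20 = 90%. SAP Section 4 takes non-missing data as the default denominator for percentages.

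**The case against.** The strongest reply is that this is a data-availability rule and not an outcome rule. A low FIX:C after washout is still a measurement, visits run to Week 52, and the protocol needs only two readings. Someone whose expression fades at 2-4 months would often have washed-out readings before resuming product, and could have some afterwards. Note 16 does not tie resumption to lost expression, protocol 4.1.5 answers a falling FIX:C with immunomodulation, and on-demand participants have no prophylaxis to resume. This stands. A reader might infer that the set removes treatment failures and must bias the result upward; the documents do not say that.

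Withdrawal is expected to be uncommon (protocol 7.2), missing data rare (9.1.1), and the direction of any withdrawal bias is unknown. This also stands.

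Exclusions would be partly visible. The disposition table counts subjects in each analysis set (SAP 5.1), and SAP 10.2 plans listings and a FIX:C plot for each subject. Escalation and expansion rest on participant counts, not on the PK-set mean. These points limit the harm, but the disposition table does not tie absence from the set to a reason.

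The sizes are assumed. The earlier study used a different vector, and protocol Appendix 6 says that the immune reaction responded to corticosteroids in prior studies and in the Phase 1/2a study. A further analysis set and some SAP text are redacted and may add detail.

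None of this justifies the joint requirement for peak and antigen.

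**Conclusion.** The concern holds in a limited form. On the text, a participant without a determinable steady state leaves the peak and antigen summaries as well, even if both were measured. This conflicts with an estimand that covers everyone meeting the entry criteria. It is certain for withdrawal before the window and possible for a participant with too few washed-out readings.

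For the steady-state mean, upward bias is conditional: it arises if exclusion follows loss of expression, and there is no systematic bias if withdrawal is unrelated to expression. With 30% retained, 2% lost and 2 of 20 excluded, the PK set gives 30% against 27.2% (arithmetic) or 22.9% (geometric) for all dosed. These inputs are assumptions, not predictions for this product. What the plan lacks is a stated rule, so in an open-label study the decision on which readings are acceptable could be made after the data are seen.

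**What to change.** Change protocol 9.3 and 9.4.1 and SAP 4.3.3 and 10.2 as follows:

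1. **Peak and antigen.** Analyse both in all dosed participants with at least one eligible washed-out post-infusion sample, with no steady-state condition.
2. **Steady state.** State that washed-out readings at a low or baseline level count as a determinable steady state. Name the same analysis set in SAP 10.2 as in protocol 9.4.1.
3. **Reporting.** Give the number excluded from the steady-state summary by dose, with reasons. Report the counts above 5% and at or above 40% (the thresholds in protocol 4.1.3.1) with all dosed participants as denominator.
4. **Sensitivity analysis.** Over all dosed participants, assign the pre-treatment baseline level to those without a determinable steady state after documented loss of expression. Take baseline before the Day 0 FIX product infusion, because SAP Section 4 defines it only as the last usable measurement before the vector. Define documented loss in advance. Count separately those who withdraw without it, since they receive no value. This belongs in a sensitivity analysis because assigning baseline can understate residual expression.

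The cost is wording, a little extra analysis and possibly a lower reported level. The infusion log records a reason for each FIX use (protocol 6.5.1), but the documents do not show that it separates lost expression from other reasons, so documented loss is better defined from the FIX:C readings.
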